11.3.2 Statistical Methods

Clinical laboratory tests will be summarized by treatment arm (A and B) at each visit during the DB Treatment Period and separately for Arm B subjects during the OL Treatment Period. Also, summaries of clinical laboratory data collected during the Post-Treatment Period will be presented for Arm A of the safety population and separately for the OL population.

The baseline value for clinical laboratory tests will be the last non-missing measurement on or before the day of the first dose of DB study drug. Values on Day 1 must also be before the time of first dose if time is available. The same baseline value will be used for all summaries of the data from the DB, OL, and Post-Treatment Period visits.

Changes from baseline to each post-baseline visit, including applicable post-treatment visits, will be summarized. For DB Treatment Period visits and for Post-Treatment visits for Arm A, each protocol-specified laboratory parameter will be summarized with the sample size; baseline mean; visit mean; and change from baseline mean, standard

deviation, and median. The differences between the active and placebo arms in the DB Treatment Period will be analyzed using an ANOVA model with treatment arm as the factor. The difference between the treatment arms (Arm A minus Arm B) in mean change from baseline along with the corresponding 95% CI, standard error, and *P* value will be presented. For OL Treatment Period visits and Post-Treatment visits for Arm B, each protocol-specified laboratory parameter will be summarized with the sample size; baseline mean; visit mean; and change from baseline mean, standard deviation, minimum, median, and maximum.

Plots of mean change (\pm standard error) from baseline to each visit will be presented by treatment arm for ALT and bilirubin (total, direct, and indirect). For each parameter, mean changes at visits during the DB Treatment Period for Arms A and B along with mean changes at post-treatment visits for Arm A will be presented on the same plot, and mean changes at visits during the OL Treatment Period will be provided for Arm B on a separate plot.

Hematology and chemistry data values will be categorized as low, normal, or high based on the normal ranges of the laboratory used for each sample. Shift tables from baseline to minimum value and from baseline to maximum value during the DB and OL Treatment Periods will be created for each treatment arm. The shift tables will cross-tabulate the frequency of subjects with baseline values below/within/above the normal range versus minimum/maximum post-baseline values below/within/above the normal range.

The laboratory parameters listed in [Table 15](#) will be categorized according to the toxicity grades defined in the table. The number and percentage of subjects with a maximum toxicity grade of 1, 2, 3 or 4 during treatment (DB treatment and OL treatment summarized separately) will be calculated for each treatment arm. To be counted, the post-baseline value must have a toxicity grade that is more extreme than the toxicity grade corresponding to the baseline value. For each laboratory parameter in [Table 15](#), the summary will also include the number and percentage of subjects with a maximum of at least Grade 3 for each treatment arm. For summaries of data collected during the DB Treatment Period, the difference in rates between the 2 arms (Arm A minus Arm B), and

the 2-sided 95% CI for the rate difference using the Wilson score method for a difference in proportions will be presented.¹² These summaries will also be presented for the set of HCV/HIV co-infected subjects (determined at Screening) within the populations/groups specified in Section 11.1.

A listing of all relevant laboratory parameters will be provided for each subject who had an increase to Grade 2 or higher for any laboratory variable in Table 15.

For the assessments of hepatotoxicity based on single and multiple laboratory parameters, the number and percentage of subjects meeting the criterion during treatment will be calculated for each criterion. A listing of all ALT, AST, total, indirect and direct bilirubin, ratio of direct to total bilirubin, and alkaline phosphatase values will be provided for each subject who met any of the single or multiple criteria defined above. The listings will be reviewed to assess bilirubin (e.g., mixed or direct predominance) and temporal relationships for subjects with $ALT > 3 \times ULN$ (or ALT Grade 2+) and total bilirubin $\geq 2 \times ULN$.

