### **8.1.5.2 Clinical Laboratory Data**

Clinical laboratory test values will be summarized by treatment group at each visit during the DB Treatment Period and separately for subjects treated in the OL Treatment Period. The baseline value will be the last measurement on or before the day of the first dose of double-blind study drug. This same baseline value will be used for all summary tables in the DB, OL, and Post-Treatment Periods.

Change from baseline to each post-baseline visit, including Final DB and OL Treatment Visits and applicable post-treatment visits, will be summarized for each protocol-specified laboratory parameter by treatment group; the baseline and visit means will be calculated along with the mean, standard deviation, and median for the change from baseline. The differences between the active and placebo arms in the DB Treatment Period will be analyzed using an ANOVA model with treatment arm as the factor. Separate tables will be used to summarize the changes from baseline to the DB Treatment Period visits (Arms A and B), the OL Treatment Period visits (Arm B), and the Post-Treatment Period visits (Arms A and B).

During the DB and OL Treatment periods, laboratory test values will be categorized as low, normal, or high based on reference ranges of the laboratory used in this study. Shift tables from baseline to minimum value and from baseline to maximum value during the DB and OL Treatment periods will be created. The shift tables will cross-tabulate, by treatment arm, the frequency of subjects with baseline values below/within/above the normal range versus minimum/maximum values below/within/above the normal range.

In addition, the number and percentage of subjects with post-baseline values during the DB and OL Treatment periods meeting pre-specified criteria for potentially clinically significant laboratory values or toxicity grades will be presented by treatment arm. Comparisons between arms will be performed on the percentage of subjects with laboratory abnormalities (by potentially clinically significant criterion or toxicity grade) during the DB Treatment Period for each parameter using Fisher's exact tests.

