4.2 Design Diagram

This is a Phase 3, randomized, double-blind, placebo-controlled multicenter study to evaluate the efficacy and safety of ABT-493/ABT-530 in non-cirrhotic chronic HCV GT1 to GT6-infected Asian adult subjects with or without HIV co-infection who are HCV treatment-naïve or treatment-experienced with IFN (alpha, beta or pegIFN) with or without RBV OR sofosbuvir with RBV with or without IFN. This study consists of a Double-Blind (DB) Treatment Period, an Open-Label (OL) Treatment Period, and a Post-Treatment (PT) Period. The study schematic is presented in [Figure 1](#).

The study is designed to enroll approximately 504 subjects to meet scientific and regulatory objectives without enrolling an undue number of subjects in alignment with scientific and ethical considerations. A minimum of 150 GT1-infected subjects, a minimum of 150 GT2-infected subjects and approximately 60 GT3, 4, 5 or 6-infected subjects from China will be enrolled into this study. Approximately 105 GT1-infected subjects and approximately 39 GT2-infected subjects will also be enrolled into this study from the regional Asian countries of South Korea and Singapore. Of the approximately 504 subjects, a maximum of 50 HCV/HIV co-infected subjects will be enrolled.

Figure 1. Study Schematic

Chronic HCV GT1 – 6 infected adults without underlying cirrhosis will be enrolled into one of two treatment arms:

Arm A: ABT-493/ABT-530 300 mg/120 mg QD for 8 or 16 weeks

Arm B: Matching Placebo for 8 or 16 weeks followed by open-label ABT-493/ABT-530 300 mg/120 mg QD for 8 or 16 weeks

All subjects in this study are to be non-cirrhotic. Treatment experienced GT3-infected subjects will receive 16 weeks of treatment in the DB and/or OL Treatment Period; all other subjects will receive 8 weeks of treatment in the DB and/or OL Treatment Period.

In China, subjects will be randomized to receive active treatment (Arm A) or placebo (Arm B) in a 2:1 ratio for each of the GT1 and GT2-infected groups and the combined GT3 to GT6 infected group. In each regional Asian country, each of the GT1 and GT2 infected groups will be randomized in a 2:1 ratio.

Subjects who are randomized to Arm B will receive open-label ABT-493/ABT-530 300 mg/120 mg QD for 8 or 16 weeks following the DB Treatment Period.

Randomization of subjects will be stratified by geographic region (China, Singapore and South Korea), genotype (GT1, GT2, combined GT3 – 6), and HCV/HIV co-infection status (yes, no).

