6.0 Analysis Conventions

6.1 Definition of Baseline, Final Treatment, and Final Post-Treatment Assessments

6.1.1 Baseline

The baseline value refers to the last non-missing measurement collected before the first dose of study drug is received. The protocol specifies that all Day 1 assessments (other than intensive PK samples) are to be performed prior to administering the first dose of study drug. Therefore, all Day 1 assessments for which time is not collected will be assumed to be pre-dose and the baseline value will be the last non-missing measurement collected on or before the first day of study drug administration.

All Day 1 assessments with time available must be before the time of first dose to be considered baseline, and the last non-missing measurement collected before the date and time of the first dose of study drug will be considered the baseline value. Only for resistance analyses, the last sample collected before OL Day 1 will be considered the baseline value for Arm B subjects. If multiple measurements that are prior to dosing are recorded on the same date and with the same time or if time is not available, then the average of these measurements will be considered the baseline value. The same baseline value will be used for analyses of the Treatment and PT Periods.

Safety assessments that are related to a serious adverse event that occurred on the first dose day are excluded when applying this algorithm.

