During the DB Treatment Period, the Final DB Treatment Value is defined separately for placebo and active subjects. Subjects randomized to placebo (Arm B) should take the first dose of OL study drugs the day immediately after the last day of the DB Treatment Period. Therefore, for Arm B subjects, the Final DB Treatment Value is defined as the last non-missing measurement collected after DB Study Day 1 and no more than 2 days after the last dose of placebo and before OL Day 1 (if applicable). For subjects randomized to active study drug (Arm A), the Final DB Treatment Value is defined as the last non-missing measurement collected after DB Study Day 1 and within 2 days of the last dose of active study drug (i.e., on or before Active Study Drug End Day 2).

During the OL Treatment Period, for subjects randomized to placebo who receive OL study drug, the Final OL Treatment Value is defined as the last non-missing measurement collected after OL Day 1 and on or before Active Study Drug End Day 2.

Final Post-Treatment Value

The final PT value for each subject is the last non-missing measurement collected after Active Study Drug End Day 2 and on or before Active Study Drug End Day 999.

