11.4.2 Statistical Methods

Vital signs will be summarized by treatment arm at each visit during the DB Treatment Period and separately for Arm B subjects in the OL Treatment Period. Also, vital signs collected during the Post-Treatment Period will be presented for Arm A of the safety population and separately for the OL population.

The baseline value for vital signs will be the last measurement on or before the day of the first dose of DB study drug. The same baseline value will be used for all summaries of the data from the DB, OL, and Post-Treatment Period visits.

Changes from baseline to each post-baseline visit, including applicable post-treatment visits, will be summarized. For DB Treatment Period visits and for Post-Treatment visits for Arm A, each vital sign parameter will be summarized with the sample size; baseline mean; visit mean; and change from baseline mean, standard deviation, and median. The differences between the active and placebo arms in the DB Treatment Period will be analyzed using an ANOVA model with treatment arm as the factor. The difference between the treatment arms (Arm A minus Arm B) in mean change from baseline along with the corresponding 95% CI, standard error, and *P* value will be presented. For OL Treatment Period visits and Post-Treatment visits for Arm B, each vital sign parameter

will be summarized with the sample size; baseline mean; visit mean; and change from baseline mean, standard deviation, minimum, median, and maximum.

The number and percentage of subjects with on-treatment values (DB treatment and OL treatment summarized separately) meeting the specified criteria for PCS vital sign values (Table 16) will be calculated for each treatment arm. A post-baseline value must be more extreme than the baseline value to be considered a PCS finding. A separate listing will be provided that presents all vital sign values for the subjects meeting PCS criteria during treatment.

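### Arm B open-label laboratory and vital-sign changes are measured from before the placebo period, so the open-label toxicity counts mix placebo-period change with on-drug change

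*SAP*

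**What the plan says.** Arm B receives "Matching Placebo for 8 or 16 weeks followed by open-label ABT-493/ABT-530 300 mg/120 mg QD for 8 or 16 weeks" (SAP 4.2). The 16-week duration applies only to treatment-experienced GT3 subjects. These subjects "should take the first dose of OL study drugs the day immediately after the last day of the DB Treatment Period" (SAP 6.1.2).

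The laboratory baseline is "the last non-missing measurement on or before the day of the first dose of DB study drug" (SAP 11.3.2), and the section continues: "The same baseline value will be used for all summaries of the data from the DB, OL, and Post-Treatment Period visits". For vital signs, SAP 11.4.2 says: "The baseline value for vital signs will be the last measurement on or before the day of the first dose of DB study drug", again carried through all periods. Protocol 8.1.5.2 has the same rule for laboratory data, "This same baseline value will be used for all summary tables in the DB, OL, and Post-Treatment Periods", and 8.1.5.4 repeats it for vital signs.

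Laboratory toxicity grades are summarized separately for double-blind and open-label treatment, and a value counts only if it meets this condition: "the post-baseline value must have a toxicity grade that is more extreme than the toxicity grade corresponding to the baseline value" (SAP 11.3.2).

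The SAP makes one exception to the common baseline, in 6.1.1: "Only for resistance analyses, the last sample collected before OL Day 1 will be considered the baseline value for Arm B subjects".

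**The concern.** For Arm A, the last value before the first double-blind dose is also the last value before active drug. For Arm B it is not: a placebo period lies between that value and the first active dose. Any open-label summary that subtracts the baseline, or asks whether a value is worse than baseline, therefore covers two periods, only one of them on drug.

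The distortion can go either way. A subject whose ALT grade rose on placebo can be counted as an open-label worsening although nothing changed on drug. A subject whose grade fell on placebo and rose again on drug to the Day 1 grade is left out.

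The open-label period is the study's only active-drug exposure outside Arm A. For subjects on the 8-week schedule, open-label Weeks 1 to 8 lie 9 to 16 weeks after the baseline value, against 1 to 8 weeks in Arm A. Even an informal side-by-side reading of the two active groups is therefore uneven.

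**Working it through.** **Size of the group.** 504 subjects at 2:1 gives 504 × 1/3 = 168 in Arm B, as in SAP Table 1. No other planned figure enters this point.

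**Mean change.** For each Arm B subject:

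OL value − DB baseline = (OL value − last pre-OL value) + (last pre-OL value − DB baseline).

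The second bracket contains no active-drug exposure. It enters the open-label mean change one for one. Against the last pre-OL value it drops out.

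**Counting rules.** The ALT grade limits are those of SAP Table 15 (Grade 1 above 1 to 3 × ULN, Grade 2 above 3 to 5 × ULN). The subject values, in multiples of ULN, are invented to show how each rule works.

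| Rule | DB Day 1 | End of placebo | Open-label | Planned baseline | Pre-OL baseline |
|---|---|---|---|---|---|
| ALT grade | 2 (Gr 1) | 4 (Gr 2) | 4 (Gr 2) | counted | not counted |
| ALT grade | 4 (Gr 2) | 2 (Gr 1) | 4 (Gr 2) | not counted | counted |
| ALT > 5 × ULN and ≥ 2 × baseline | 3 | 6 | 6 | met (2 × 3 = 6) | not met (2 × 6 = 12) |
| Total bilirubin ≥ 2 × ULN and > baseline | 1.5 | 2.2 | 2.1 | met | not met |

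Shift tables and the vital-sign criteria of SAP Table 16 also compare with the same baseline.

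**Rules not tied to DB Day 1.** The criterion for ALT increase by grade, and the ALT part of the combined ALT/bilirubin criterion, use the first nadir, which may be baseline or a later value (SAP 11.3.1). The bilirubin part of the combined criterion ignores baseline. The SAP does not say whether the nadir search restarts at open-label Day 1.

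**Illustration of size.** The documents give no drift or variance, so every input here is an assumption: ALT with median 1.5 × ULN and log SD 0.6 at DB Day 1; normal log change over placebo with the mean and SD shown; no drug effect; log noise 0.1 in open-label; one open-label value per subject. Expected number of 168 subjects counted as worsened in grade, by simulation:

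| Mean log drift on placebo | Log SD over placebo | Against DB Day 1 | Against end of placebo |
|---|---|---|---|
| −0.2 | 0.2 | 4 | 6 |
| −0.2 | 0.4 | 14 | 6 |
| 0 | 0.2 | 15 | 7 |
| 0 | 0.4 | 28 | 7 |
| +0.2 | 0.4 | 47 | 7 |

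With zero drift the two counts still differ, and about 2 of the 7 subjects in the last column are missed by the planned rule. A small mean drift is therefore not enough to dismiss the point.

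**How strongly the size depends on the limit.** Under a bivariate normal model with an assumed correlation of 0.7 to 0.9 across the placebo period, the number of 168 crossing a limit upward on placebo alone is:

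- 12 to 21 if half of subjects exceed the limit (arccos(ρ)/2π = 0.127 at ρ = 0.7 and 0.072 at ρ = 0.9, times 168);
- 5 to 9 if 10% exceed it;
- 3 to 5 if 5% exceed it;
- 1 to 2 if 2% exceed it.

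**The case against.** The strongest reply is that this is a deliberate choice, stated alike in both documents. A single pre-treatment baseline shows each subject's whole course, and replacing it would lose change from study entry. That stands, and it is why the remedy should add tables rather than replace them.

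The reply also points to safeguards. Open-label data are descriptive, with no comparisons (Protocol 8.1.5), and apart from listings of serious events and deaths they are outside the primary report (SAP 11.1). Arm B's placebo-period results are tabulated separately. Laboratory values are listed for subjects rising to Grade 2 or higher, and liver values for subjects meeting a hepatotoxicity criterion. These help with individual cases and let a reader roughly net out mean drift. They do not correct the aggregate shift, grade or vital-sign counts.

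Three stronger readings are tempting but not supported:

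- A reader might infer that every hepatotoxicity criterion rests on DB Day 1. The nadir-based ALT rules and the bilirubin part of the combined rule do not.
- A reader might infer that laboratory data and vital signs are singled out while everything else restarts at open-label Day 1. The ECG baseline is the Screening tracing for both periods (Protocol 5.3.1.1), and CD4/CD8 changes have no open-label reset (SAP 6.1.1, 11.5). Resistance is the one expressly worded exception. Adverse events are dated by onset and have no baseline value to reset.
- A reader might take 12 to 21 of 168 as the number miscounted. That range needs a limit that half of subjects exceed, and it counts crossings on placebo, which matter only if they persist into open-label. Protocol 3.0 reports that elevated ALT moved toward normal on treatment in Phase 2, so false open-label ALT worsening is likely to be rarer than a no-drug-effect model suggests.

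**Conclusion.** The point holds as a limited one. Under the planned baseline, open-label mean changes, shift tables, worsening-grade counts, the two baseline-referenced ALT and bilirubin criteria (the bilirubin one with or without its direct/total ratio condition) and the vital-sign counts mix placebo-period with on-drug change. This follows from the definitions and needs no assumption. Whether the nadir-based ALT rules are affected cannot be settled, because the SAP does not define where the nadir starts in open-label.

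The size is unknown. The illustrative 4 to 47 counted subjects against 6 to 7 rests wholly on assumed drift and variance, and the error can be an overcount or an undercount. It is not an estimate for this trial, and it does not carry over to vital signs, where most criteria need an extreme absolute value as well as a change.

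The primary endpoint, the randomized double-blind safety comparison and adverse-event counting are unaffected. The two documents do not contradict each other. This is a cheap improvement to descriptive safety tables, not a flaw that threatens the trial's conclusions.

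**What to change.** Keep DB Day 1 as the common baseline for trajectory summaries. In SAP 6.1.1, 11.3.1, 11.3.2 and 11.4.2:

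- Define a second baseline for the open-label population: the last non-missing value before the first open-label dose. Do not simply reuse the Final DB Treatment Value. That value must fall within 2 days of the last placebo dose, so a subject who stops placebo early but stays on for open-label treatment may have a later panel.
- Add open-label change-from-baseline, shift, toxicity-grade, baseline-referenced hepatotoxicity and vital-sign summaries against this value, and name these as the on-drug open-label toxicity counts.
- State that the ALT nadir for open-label starts from this value.
- Record the addition in SAP 12.1, where departures from the protocol are already listed.

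No new data are needed: Protocol Appendix C schedules laboratory tests and vital signs at the final double-blind visit, and open-label dosing is planned for the next day. The cost is a second baseline variable for Arm B and a set of extra tables. The added tables would not remove time effects within the uncontrolled open-label period itself.

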## **8.0 Statistical Methods and Determination of Sample Size**

### **8.1 Statistical and Analytical Plans**

The primary analysis will occur after all subjects in Arm A have completed the PT Week 12 Visit or prematurely discontinued the study. The primary analysis will summarize data through PT Week 12 for Arm A subjects and data through the DB Treatment Period for Arm B subjects. The data for the primary analysis will be locked after data cleaning, and data collected after this lock will be added to a new version of the database. Results from the primary analysis will be described in the primary clinical study report (CSR) and submitted to regulatory agencies as part of an NDA submission. An interim analysis will occur after all Arm A subjects have completed the PT Week 24 Visit or prematurely discontinued the study and all Arm B subjects have completed the PT

Week 12 Visit or prematurely discontinued the study. The data for the interim analysis will be locked after data cleaning. Data collected after this lock will be added to a new version of the database which will be cleaned and locked at the end of the study.

SAS® (SAS Institute, Inc., Cary, NC) for the UNIX operating system will be used for all analyses. All statistical tests and confidence intervals will be two-sided with an alpha level of 0.05. Descriptive statistics will be provided, such as the number of observations (N), mean, and standard deviation (SD) for continuous variables and counts and percentages for categorical variables.

Analyses will be performed on the intent-to-treat (ITT) population defined as all randomized subjects who receive at least one dose of study drug in the DB Treatment Period, unless otherwise specified. The primary and secondary efficacy endpoints will be analyzed on the ITT population treated with active study drug in the DB Treatment Period (Arm A). Sensitivity analyses of the primary efficacy endpoint, when applicable, will be performed on the ITT population modified to exclude subjects of multiple GTs according to the central laboratory or phylogenetic analyses (mITT-GT), and on the mITT-GT population modified to exclude subjects who did not achieve SVR12 for reasons other than virologic failure (mITT-GT-VF). In addition, some analyses will be performed on the OL Population defined as all subjects who receive at least one dose of study drug during the OL Treatment Period.

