### **8.1.5.4 Vital Signs Data**

Vital signs will be summarized by treatment group (DB active and DB placebo) at each visit during the DB Treatment Period and separately for subjects treated in the OL Treatment Period. The baseline value will be the last measurement on or before the day of the first dose of double-blind study drug. This same baseline value will be used for all summary tables in the DB, OL, and Post-Treatment Periods.

Mean changes in temperature, systolic and diastolic blood pressure, pulse, and weight from baseline to each post-baseline visit, including Final DB and OL Treatment Visits, will be summarized descriptively by arm. The differences between the active and placebo arms in the DB Treatment Period will be analyzed using contrasts within an ANOVA model with treatment arm as the factor. Frequencies and percentages of subjects with post-baseline values meeting pre-defined criteria for potentially clinically significant vital sign values will be summarized by treatment arm, separately for the DB and OL Treatment Periods. Comparisons between arms will be performed on the percentage of subjects experiencing a value meeting the criteria during the DB Treatment Period for each parameter using Fisher's exact tests.

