10.9 Patient Reported Outcomes

The following instruments will be used to collect patient reported outcomes (PROs): EuroQol-5 Dimensions-3 Level (EQ-5D-3L) and Fatigue Severity Scale (FSS).

Subject's responses to the EQ-5D-3L will be combined into a unique health state using a 5-digit code with 1 digit from each of the 5 dimensions. The EQ-5D-3L states will be converted into a single preference-weighted health utility index score by applying weights.^{10,11} The VAS score will be analyzed separately. For EQ-5D-3L index and VAS scores, no imputation will be performed for missing items.

The FSS measures the impact of fatigue over the past week on specific types of functioning. The survey consists of 9 questions using a 7-point Likert scale. A total score is calculated as the average of the individual item responses (adding up all the answers and dividing by nine). Higher FSS scores indicate a higher degree of impact of fatigue. Imputation will be applied to the total score as described in Section 6.3.

Summary statistics (n and mean,) at each protocol-specified visit and for change from baseline (n, mean, SD, minimum and maximum) to each protocol-specified visit will be provided for the EQ-5D-3L health index score and VAS score and for the FSS total score for each treatment arm in the ITT population (as applicable). For each of these scores, mean change from Baseline to the final scheduled DB Treatment Period Visit (Week 8 or Week 16) will be compared between treatment arms using an analysis of covariance (ANCOVA) model with treatment arm as a factor and baseline score as a covariate.

The number and percentage of subjects who have ever experienced an increase from baseline up through each applicable time point of greater than or equal to 0.7 in the FSS total score will also be calculated for each treatment arm in the ITT population (as applicable), along with two-sided 95% CIs based on the normal approximation to the binomial distribution. In addition, percentages of subjects meeting the criteria at each applicable time point during the DB Treatment Period will be compared between Arm A and Arm B using Fisher's Exact Test.

If a subject starts another treatment for HCV, then all PRO values for this subject measured on or after the start date of the new HCV treatment will be excluded from analyses.

The analyses described above will also be performed for the geographic region of China.

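### Laboratory and vital-sign changes are compared between arms without a baseline covariate: the test is valid, but less precise than the ANCOVA the SAP already uses for PROs

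*SAP*

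**What the plan says.** **Laboratory data.** SAP 11.3.2 analyses change from baseline at each visit. The quantity reported is "The difference between the treatment arms (Arm A minus Arm B) in mean change from baseline", with a 95% CI, standard error and P value. The model's only term is treatment arm: "active and placebo arms in the DB Treatment Period will be analyzed using an ANOVA model with treatment arm as the factor". Protocol 8.1.5.2 has the same model: "analyzed using an ANOVA model with treatment arm as the factor".

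**Vital signs.** SAP 11.4.2 repeats the method: differences "between the active and placebo arms in the DB Treatment Period will be analyzed using an ANOVA model with treatment arm as the factor". Protocol 8.1.5.4 agrees: "analyzed using contrasts within an ANOVA model with treatment arm as the factor".

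**PROs.** In SAP 10.9, change in the EQ-5D-3L and FSS scores is "compared between treatment arms using an analysis of covariance (ANCOVA) model with treatment arm as a factor and baseline score as a covariate".

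Protocol 8.1 sets the general level: "All statistical tests and confidence intervals will be two-sided with an alpha level of 0.05". No section adds a baseline-adjusted sensitivity analysis for laboratory or vital-sign change, and none gives a reason for treating these changes differently from the PRO changes.

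**The concern.** The baseline value is collected and is used as a covariate for one set of continuous change endpoints but not for the other. A change score fixes the coefficient of baseline at 1. When the within-arm slope of follow-up on baseline is below 1, subtraction over-corrects. The comparison then carries avoidable variance, and a chance baseline difference between arms passes into the estimate with its sign reversed.

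Dependence of change on baseline is plausible for ALT: protocol 3.0 reports that elevated baseline ALT moved to or towards normal on active drug. The ANOVA results also stand alone as tests. SAP 12.1 removed Fisher's exact tests from the AE, laboratory-grade and vital-sign summaries, which leaves the ANOVA P values as the only between-arm P values in SAP Section 11.

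At stake are the width of these intervals and how they read in a trial whose baseline happens to be unbalanced. No efficacy conclusion is at stake.

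**Working it through.** **Inputs.** Arm sizes are 336 (Arm A) and 168 (Arm B), from SAP 4.3 and its Table 1. The documents state no SD, correlation or power for these comparisons, so there is no plan figure to reproduce. Assumptions: ρ from 0.3 to 0.9, equal baseline and follow-up SD (σ), and a common slope in both arms.

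**Precision.** Let f = 1/336 + 1/168, so √f = 0.0945.

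- Change-score ANOVA: variance = 2σ²(1−ρ)f
- ANCOVA: variance = σ²(1−ρ²)f
- Ratio = 2(1−ρ)/(1−ρ²) = 2/(1+ρ)

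| ρ | SE, ANOVA (SD) | SE, ANCOVA (SD) | Variance ratio | CI wider by | 504 subjects worth, under ANCOVA | ANOVA power where ANCOVA has 80% |
|---|---|---|---|---|---|---|
| 0.3 | 0.1118 | 0.0901 | 1.538 | 24.0% | 328 | 62% |
| 0.5 | 0.0945 | 0.0818 | 1.333 | 15.5% | 378 | 68% |
| 0.7 | 0.0732 | 0.0675 | 1.176 | 8.5% | 428 | 73% |
| 0.9 | 0.0423 | 0.0412 | 1.053 | 2.6% | 479 | 78% |

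**Carry-over of imbalance.** The chance baseline difference has SE 0.0945 SD, so its 95% range is ±1.96 × 0.0945 = ±0.185 SD. The change score passes on −(1−ρ) of it. At the 95% limit this is 0.130 SD (ρ = 0.3), 0.093 SD (0.5), 0.056 SD (0.7) and 0.019 SD (0.9). In the China-only safety analyses, planned at 240:120, the SE of the baseline difference is √(1/240 + 1/120) = 0.112 SD.

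**Simulation.** 20,000 trials were run at each of two correlations, with 336:168 subjects and no treatment effect.

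- Variance ratios were 1.34 (ρ = 0.5) and 1.18 (ρ = 0.7), as the formula predicts.
- Overall type I error of the ANOVA was 4.9% and 5.1%.
- Among trials with a baseline imbalance beyond 1.96 SE, it was 20% and 13%, against about 5% for ANCOVA.

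**Unequal slopes, the plausible ALT case.** Take baseline variance 1, m placebo and 2m active subjects, slopes a (active) and b (placebo), and a residual contribution R/m common to all the estimators.

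- Change score: [(a−1)²/2 + (b−1)² + R]/m
- Common-slope ANCOVA: the pooled slope is (2a+b)/3, which gives [(b−a)²/2 + R]/m
- Arm-specific slopes, centred at the overall mean: [(b−a)²/3 + R]/m

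With a = 0 and b = 1 the three slope terms are 0.5, 0.5 and 0.333. Common-slope ANCOVA then gains nothing over the change score, while arm-specific slopes do gain. With a = 0 and b = 0.7 the first two terms are 0.5 + 0.09 = 0.59 and 0.49/2 = 0.245. The gain returns, by an amount that depends on R.

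**The case against.** The strongest reply is that little depends on these tests. They carry no power claim, success rule or multiplicity role. The safety summaries that matter clinically already use each subject's baseline: shift tables, toxicity grades that must be worse than at baseline, ALT criteria relative to baseline or nadir, and vital-sign criteria defined by change. Baseline values are also compared between arms under SAP 7.1, so an imbalance would be visible. All of this stands and keeps the severity low. None of it adjusts the mean-change differences, intervals or P values.

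Some stronger readings are tempting, but the documents do not support them.

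- *Baseline is ignored.* It is not. It is subtracted, and baseline means are displayed.
- *The test is biased by regression to the mean.* That effect acts on both randomized arms and cancels on average. It matters only through chance imbalance, so it is not a second defect.
- *A loss of 18–54% is established.* That range belongs to assumed correlations of 0.7 to 0.3. At 0.9 the excess is about 5%.
- *The gain for ALT must be larger still.* If the follow-up SD shrank equally in both arms, with a baseline-to-follow-up SD ratio of 1.5 to 2 and ρ of 0.3 to 0.7, the variance ratio would be about 2.2 to 4.3. Normalization is expected on active drug, though, and not on placebo. With unequal slopes the common-slope gain can be nil.
- *Leaving out the randomization factors is a comparable fault.* Nothing in the documents sizes that effect. SAP 12.1 does not expect genotype to affect safety, and the PRO baseline covariate may already absorb part of any regional difference in level.

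**Conclusion.** The point holds as a low-severity, free improvement. The planned ANOVA is valid on average. Given a baseline imbalance it is less precise and less reliable than the ANCOVA already specified for PROs. With equal variances and a common slope, the excess variance is 54%, 33%, 18% and 5% at ρ = 0.3, 0.5, 0.7 and 0.9, and the intervals are 24% to 2.6% wider. These sizes rest on assumed correlations and will differ by parameter. For ALT and bilirubin, where slope and spread may differ by arm under 2:1 allocation, the common-slope figures should not be relied on.

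**What to change.** In SAP 11.3.2 and 11.4.2, replace the ANOVA with an ANCOVA on change from baseline, with treatment arm and baseline value as terms. Keep the raw baseline, visit and change means in the tables. For ALT and bilirubin, include a mean-centred baseline-by-arm term and use robust standard errors.

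Because protocol 8.1.5.2 and 8.1.5.4 prespecify the ANOVA, list the change in SAP 12.1 before the primary-analysis lock. Earlier is better, since assignments are unblinded subject by subject at the end of double-blind treatment.

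Adding randomization factors to these models and to the PRO ANCOVA is optional. If it is done, it should account for all three: region, genotype group and HIV co-infection status.

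The cost is a change of model statement, some table programming and one entry in the list of changes. No new data are needed.
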